6.5 Duplicate Patients

Patients found to have been enrolled more than once during the study (either at same site or different sites) will only have screenings/visits associated with their first enrollment counted in the study population. Any additional screenings/enrollments/visits attached to a subsequent enrollment (or attempted enrollment) will be excluded from all analyses and analysis populations.

7.1 Derived Variables

The below table provides a list of derived variables for demographic and baseline characteristics.

Variables	Formula
Demographic and Baseline characteristics	
Age at informed consent (in years)	integer ((date of informed consent – date of birth + 1)/365.25)
Body mass index (BMI) (kg/m ²)	weight (kg)/[height (m)]^2
Patient-Reported Outcome Scoring	
PROMIS SexFS Pain Subscale (vaginal discomfort)	
In the last 30 days
 
Question SFSCR202:
 
Did you have any type of sexual activity?
 
1=No 2=Yes
 
Question SFVAG202:
 
When you have had sexual activity, how much discomfort have you felt inside your vagina?
 
1=None 2=A little bit 3=Some 4=Quite a bit 5=A lot
 
Question SFVAG206:
 
When you have had sexual activity, how much pain have you felt inside your vagina?
 
1=None 2=A little bit 3=Some 4=Quite a bit 5=A lot
 
Scoring conversion table Conditional on 2=yes for SFSCR202

Vaginal Discomfort for Sexual Activity Short Form Conversion Table			
SFVAG202	SFVAG206	T-Score	SE ¹
1	1	43.3	6.6
1	2	52.8	2.6
1	3	55.6	3.4
1	4	56.8	4.3
1	5	57.3	4.8
2	1	53.3	2.6
2	2	56.9	2.5
2	3	60.4	2.5
2	4	62.5	3.1
2	5	63.6	3.9
3	1	57.3	3.2
3	2	60.9	2.4
3	3	63.8	2.2
3	4	66.4	2.4
3	5	68.3	3.1
4	1	59.8	4.4
4	2	63.7	3.0
4	3	66.8	2.3
4	4	69.9	2.4
4	5	73.0	2.5
5	1	61.9	5.7
5	2	66.2	4.2
5	3	69.9	3.1
5	4	73.6	2.5
5	5	78.1	3.4

¹SE= Standard Error

PROMIS SexFS Lubrication Subscale	
In the last 30 days
 
Question SFSCR202:
 
Did you have any type of sexual activity?
 
1=No 2=Yes
 
Question SFLUB001:
 
How often did you become lubricated (“wet”) during sexual activity or intercourse?
 
5=Almost always or always 4=Most of the time (more than half the time) 3=Sometime (about half the time) 2=A few time (less than half the time) 1=Almost never or never
 
Question SFLUB004:
 
How difficult was it to maintain your lubrication (“wetness”) until completion of sexual activity or intercourse?
 
1=Extremely difficult or impossible 2=Very difficult 3=Difficult 4=Slightly difficult 5=Not difficult
 
Scoring conversion table Conditional on 2=yes for SFSCR202

-----------------------------------	-----------------------------------------------------------------------------------------------------------------------------------------------------------------------------------------------------------------------------------------------------------------------------------------------------------------------------------------------------------------------------------------------------------------------------------------------------------------------------------------------------------------------------------------------------------------------------------------------------------------------------------------------------------------------------------------------------------------------------------------------------------------------------------------------------

Vaginal Lubrication for Sexual Activity Short Form Conversion Table			
SFLUB004	SFLUB001	T-Score	SE ¹
1	1	27.6	4.5
1	2	32.0	3.8
1	3	34.2	4.2
1	4	35.8	4.9
1	5	37.7	5.9
2	1	33.1	3.3
2	2	35.4	3.1
2	3	37.2	3.4
2	4	38.8	3.9
2	5	40.7	4.9
3	1	36.2	3.3
3	2	38.0	3.0
3	3	39.5	3.0
3	4	41.1	3.4
3	5	43.1	4.3
4	1	40.3	4.0
4	2	41.8	3.5
4	3	43.4	3.3
4	4	45.4	3.4
4	5	48.1	3.8
5	1	47.4	4.9
5	2	48.1	4.5
5	3	49.2	4.2
5	4	51.2	4.0
5	5	58.4	6.5

¹SE: Standard Error

FSFI Pain Subscale

FSFI Q17:

Over the past 4 weeks, how often did you experience pain during vaginal penetration?

- 0=Did not attempt intercourse
- 1=Almost always or always
- 2=Most times (more than half the time)
- 3=Sometimes (about half the time)
- 4=A few times (less than half the time)
- 5=Almost never or never

FSFI Q18:

Over the past 4 weeks, how often did you experience pain following vaginal penetration?

- 0=Did not attempt intercourse
- 1=Almost always or always
- 2=Most times (more than half the time)
- 3=Sometimes (about half the time)
- 4=A few times (less than half the time)
- 5=Almost never or never

	
FSFI Q19:
 
Over the past 4 weeks, how would you rate your level (degree) of discomfort or during or following vaginal penetration?
 
0=Did not attempt intercourse 1=Very high 2=High 3=Moderate 4=Low 5=Very low or none at all
 
Pain Score = (FSFIQ17+ FSFIQ18+ FSFIQ19)*0.4

FSFI SexFS Lubrication Subscale	
FSFI Q7:
 
Over the past 4 weeks, how often did you become lubricated (“wet”) during sexual activity or intercourse?
 
0=No sexual activity 1=Almost always or always 2=Most times (more than half the time) 3=Sometimes (about half the time) 4=A few times (less than half the time) 5=Almost never or never
 
FSFI Q8:
 
Over the past 4 weeks, how difficult was it to become lubricated (“wet”) during sexual activity or intercourse?
 
0=No sexual activity 1=Extremely difficult or impossible 2=Very difficult 3=Difficult 4=Slightly difficult 5=Not difficult
 
FSFI Q9:
 
Over the past 4 weeks, how often did you maintain your lubrication (“wetness”) until completion of sexual activity or intercourse?
 
0=No sexual activity 1=Almost always or always 2=Most times (more than half the time) 3=Sometimes (about half the time) 4=A few times (less than half the time) 5=Almost never or never
 
FSFI Q10:
 
Over the past 4 weeks, how difficult was it to maintain your lubrication (“wetness”) until completion of sexual activity or intercourse?
 
0=No sexual activity

	
1=Extremely difficult or impossible 2=Very difficult 3=Difficult 4=Slightly difficult 5=Not difficult
 
Lubrication Score = (FSFIQ7+FSFIQ8+FSFIQ9+FSFIQ10)*0.3

--	--------------------------------------------------------------------------------------------------------------------------------------------------------------------------------------------

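### The FSFI pain score ranks women who attempted no intercourse below those with the worst pain; the lubrication score also adds the zero code, and its items run in opposite directions

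*SAP*

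**What the plan says.** SAP section 7.1 (Derived Variables) scores two FSFI domains as weighted sums of raw item codes.

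- **Pain**, items 17 to 19: "Pain Score = (FSFIQ17+ FSFIQ18+ FSFIQ19)*0.4". Items 17 and 18 ask how often pain occurred, from "1=Almost always or always" to "5=Almost never or never". Item 19 asks about its degree: "0=Did not attempt intercourse 1=Very high 2=High 3=Moderate 4=Low 5=Very low or none at all". On all three, a higher code means less pain, and 0 means that intercourse was not attempted.
- **Lubrication**, items 7 to 10: "Lubrication Score = (FSFIQ7+FSFIQ8+FSFIQ9+FSFIQ10)*0.3". Each item has the code "0=No sexual activity". Items 7 and 9 (how often lubricated, how often maintained) run from 1 for almost always to 5 for almost never. Items 8 and 10 (how difficult) run from 1 for extremely difficult to 5 for not difficult.

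Neither formula is conditional on activity. SAP 7.2.1 says that analyses other than the infection endpoints use data as observed, and a recorded 0 is an observed value.

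For the PROMIS pain and lubrication scores, the same section says "Scoring conversion table Conditional on 2=yes for SFSCR202", so a woman reporting no sexual activity gets no PROMIS score.

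SAP 4.3 lists the FSFI lubrication and pain subscales for comparison between EVO100 and placebo. SAP section 10 plans a subscale table by visit (14.2.3.5) and a subscale table of shifts from baseline (14.2.3.7).

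**The concern.** Code 0 on these items is a not-applicable answer, not a level of symptoms. Adding it into a scale whose worst symptom code is 1 puts women without intercourse at the bad end of the pain scale. The mean score then mixes pain severity with abstinence, and a difference between arms in abstinence would look like a difference in pain. A woman active at baseline who later attempts no intercourse would show a fall in her score, which reads as worsening.

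The lubrication sum takes in zeros in the same way. It also has a second fault: the item directions conflict, so the sum does not measure lubrication at all as coded.

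What is at stake is the reading of the exploratory tolerability tables for a vaginal gel, where pain and lubrication are natural things to look at.

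**Working it through.** The SAP states no score range or expected mean, so there is no figure to reproduce. The check evaluates the two formulas at the codes in SAP 7.1.

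**Pain = 0.4 × (item 17 + item 18 + item 19)**

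| Woman | Codes | Score |
|---|---|---|
| No intercourse attempted | 0, 0, 0 | 0.4 × 0 = 0.0 |
| Worst pain on every item | 1, 1, 1 | 0.4 × 3 = 1.2 |
| No pain | 5, 5, 5 | 0.4 × 15 = 6.0 |

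A woman without intercourse is 1.2 points below the worst possible pain.

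**Lubrication = 0.3 × (item 7 + item 8 + item 9 + item 10)**

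| Woman | Codes as printed | Score | Score with items 7 and 9 reversed |
|---|---|---|---|
| No activity, all items | 0, 0, 0, 0 | 0.0 | not applicable |
| Driest | 5, 1, 5, 1 | 0.3 × 12 = 3.6 | 0.3 × 4 = 1.2 |
| Best lubricated | 1, 5, 1, 5 | 0.3 × 12 = 3.6 | 0.3 × 20 = 6.0 |
| Lowest sum with activity | 1, 1, 1, 1 | 0.3 × 4 = 1.2 | – |

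For a consistent answer at level k (1 = worst, 5 = best), the printed codes are 6 − k, k, 6 − k, k. They sum to 12 for every k, so the score is always 3.6. An active woman reaches 1.2 only by a contradictory pattern: almost always lubricated, yet with extreme difficulty. The PROMIS frequency item in the same section (SFLUB001) codes almost always as 5, the reverse of FSFI items 7 and 9.

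**Effect on a mean pain score.** The documents give neither a mean nor an abstinence rate, so both are assumed. If active women average m and a share f score 0, the arm mean is m × (1 − f).

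- With m = 5.0, f = 5%, 10% or 15% gives 4.75, 4.50 or 4.25.
- With identical pain and f = 10% against 5%, the spurious difference is m × 0.05. This is 0.24 for m = 4.8, 0.25 for m = 5.0, 0.27 for m = 5.4 and 0.30 for m = 6.0.

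These figures apply to pain only. A mean of 5.0 cannot stand for a lubrication score that is 3.6 for every consistent answer.

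**The case against.** The case on the other side is substantial.

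- **No inferential weight.** The subscales are exploratory, SAP 8.6.3 gives them no test, and they are outside the hierarchy in SAP 8.6.1. Endpoints A and B use FSFI item 16. A reader might infer a threat to the primary or hierarchical endpoints; the documents show none. This stands.
- **Dryness.** A reader might infer that inactive women are counted as extremely dry. The printed coding does not support that, because 0.0 lies equally far below the driest and the best-lubricated woman. The reading would become true only once items 7 and 9 are reversed, so the zero rule is still needed then.
- **Zeros may be few.** Inclusion criterion 8 in the protocol synopsis requires intercourse at least three times in the previous month and an expectation of regular intercourse. That limits zeros at baseline, but not later ones, which are those that would read as worsening.
- **Differential abstinence after infection.** This is tempting as a mechanism but weak: under Treatment Duration in the protocol synopsis, participation runs only until a positive test. The documents give no reason to expect abstinence to differ between arms.
- **Zeros will partly be visible.** SAP 8.6.3 plans counts and percentages of responses by visit, and Table 14.2.3.6 covers all FSFI questions. The FSFI text there does not explicitly promise a summary of derived scores, as the PROMIS text does. Even so, section 7.1 defines the scores and Tables 14.2.3.5 and 14.2.3.7 are titled for the subscales.
- **PROMIS is not an identical gate.** It asks about any sexual activity in 30 days; FSFI pain code 0 concerns attempted intercourse in 4 weeks. The comparison shows a similar practice, not the same rule.
- **The instrument's own scoring rules** may sum the zeros. That cannot be checked from these documents. If they do, the zeros still need to be reported beside the score.
- **Abstinence may result from pain**, so dropping zeros could hide a signal. This is a fair point, and the fix must allow for it.

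**Conclusion.** The point holds as a minor one. For pain, SAP 7.1 gives a misleading score as written: 0.0 for no intercourse against 1.2 for the worst pain, with no rule elsewhere that removes the zeros. For lubrication, the zero is also added below the active minimum of 1.2, but the larger fault is that items 7 and 9 run opposite to items 8 and 10, so the score cannot separate the driest woman from the best lubricated. Excluding zeros alone would not mend it.

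The effect is confined to exploratory descriptive tables. The 0.25-point illustration for pain rests on an assumed mean of 5.0 in active women and an assumed 5-percentage-point difference in abstinence; neither comes from the documents. That the score mixes pain with abstinence follows from the formula alone; that abstinence will differ by arm is not shown.

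**What to change.** In SAP 7.1:

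1. Treat code 0 on items 17 to 19 and 7 to 10 as not applicable, and leave the domain score missing when any of its items is 0. This is in line with, though not identical to, the activity condition on the PROMIS scores.
2. Reverse the coding of items 7 and 9 so that all four lubrication items run from worst to best, as PROMIS item SFLUB001 does. With both changes, each score runs from 1.2 (worst) to 6.0 (best).
3. In Tables 14.2.3.5 and 14.2.3.7, show the number of zero responders by arm and visit beside the score.
4. Keep the zero-included score as supportive only, so that abstinence caused by pain is not lost from view.

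The cost is a few sentences of SAP text and no new data. The downside is slightly fewer scores per visit and a departure from the plain sum, which the SAP should state openly.

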4.3 Exploratory Endpoints

Exploratory assessments include:

- Comparison of the proportion of subjects with overall sexual satisfaction using the female sexual function index (FSFI) overall sexual satisfaction question at Visit 5 and not having a CT or GC infection.
- Comparison of the proportion of subjects with overall sexual satisfaction using the FSFI overall sexual satisfaction question at Visit 5.
- Comparison of the proportion of subjects reporting overall product satisfaction at Visit 5.

- Comparison of compliance with EVO100 vaginal gel usage versus placebo usage during study (rate of product use adherence versus placebo).
- Subgroup analyses of the primary endpoint (the proportion of subjects who are defined success versus failure) will be performed for the following:
 - Subjects with 0%, >0% and <20%, ≥20% and <40%, ≥40% and <60%, ≥60% and <80%, ≥80% and <100%, ≥80% and ≤100%, and 100% product use adherence.
- Descriptive analysis of failure components for the FDA and EMA primary endpoints.
- Comparison of PROMIS Sexual Function and Satisfaction (PROMIS SexFS), Pain and Lubrication subscales with EVO100 vaginal gel usage versus placebo.
- Comparison of FSFI Lubrication and Pain subscales with EVO100 vaginal gel usage versus placebo.
- Comparison of Patient Global Impression of Change (PGIC) with EVO100 vaginal gel usage versus placebo.

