 - Subjects with 0%, >0% and <20%, ≥20% and <40%, ≥40% and <60%, ≥60% and <80%, ≥80% and <100%, ≥80% and ≤100%, and 100% product use adherence. For the purposes of the frequency table, each compliance group will be deemed mutually exclusive.
- Similar to the FDA primary endpoint analysis, failure components of the primary endpoint (i.e., CT infection, GC infection, use of prohibited antibiotics, lost to follow-up, or invalid CT/GC test at Visit 5) will be summarized using frequencies and percentages with the difference between treatment groups analysed using a Chi-Square test. The Fisher's Exact test will be conducted in place of the Chi-Square test if necessary due to issues with the expected cell counts.
- Responses to the PROMIS SexFS Satisfaction, Pain and Lubrication subscales with EVO100 vaginal gel usage and placebo at each visit will be summarized using count and percentage. Descriptive summary will also be provided using the derived subscale scores (refer [section 7.1](#)). In addition, the shifted change from baseline to post baseline response will also be summarized.
- Response to FSFI questionnaire- Lubrication and Pain subscales with EVO100 vaginal gel usage and placebo at each visit will also be summarised using count and percentage. Response to questions 7, 8, 9, 10 will be considered for lubrication subscale and questions 17, 18 and 19 will be considered for pain subscales from the FSFI questionnaire. In addition, the shifted change from baseline to post baseline response will be summarized.
- Patient Global Impression of Change (PGIC) with EVO100 vaginal gel usage versus placebo will be summarized by treatment group.

Validation related analyses for the patient-reported outcomes (FSFI, product satisfaction questionnaire, PROMIS SexFS etc.) referenced here will be outlined in a separate psychometric analysis plan.

Listings will be provided for PROMIS SexFS, FSFI, product satisfaction questionnaire and PGIC.

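### The FSFI lubrication score in SAP 7.1 adds two items coded high = worse to two coded high = better, so uniformly best and uniformly worst answers both score 3.6

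*SAP*

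**What the plan says.** SAP 7.1 (Derived Variables) defines the FSFI lubrication subscale from four items.

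- **Q7** (how often the woman became lubricated) and **Q9** (how often lubrication lasted to completion) are both coded "0=No sexual activity 1=Almost always or always 2=Most times (more than half the time" and continue to 5 for almost never or never.
- **Q8** and **Q10** (difficulty of becoming and of staying lubricated) are coded "1=Extremely difficult or impossible 2=Very difficult 3=Difficult 4=Slightly difficult 5=Not difficult", again with 0 for no sexual activity.

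The scoring rule is "Lubrication Score = (FSFIQ7+FSFIQ8+FSFIQ9+FSFIQ10)*0.3". No reverse-scoring step appears in 7.1, or in 8.6.3, which names the same four items.

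The subscale serves a listed exploratory assessment, in the protocol synopsis and in SAP 4.3: "Comparison of FSFI Lubrication and Pain subscales with EVO100 vaginal gel usage versus placebo".

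**The concern.** A sum score needs all its items to point the same way. Here a woman with good lubrication gets low codes on Q7 and Q9 and high codes on Q8 and Q10, and the two pairs offset each other. If the data follow the printed codes, the derived score reflects the difference between the difficulty and frequency answers, not how well lubricated the woman was.

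The product is a vaginal gel, so lubrication is a natural thing to compare between arms. SAP Table 2 schedules the FSFI at all seven visits but PROMIS at only four (screening and Visits 1, 5 and 6). At Visits 2 to 4 the FSFI score is therefore the only lubrication score that 7.1 defines.

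**Working it through.** The SAP gives no worked example or score range to reproduce, so the check evaluates the printed rule on the printed codes.

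**Inputs (all SAP 7.1).** Let L be the level of an item in the favourable direction, 1 = worst and 5 = best, for sexually active women.

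- Printed code of Q7 and Q9: 6 − L.
- Printed code of Q8 and Q10: L.
- Multiplier: 0.3.

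**Formulas.**

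- Printed score = 0.3 × [(6 − L7) + L8 + (6 − L9) + L10] = 3.6 + 0.3 × [(L8 + L10) − (L7 + L9)].
- Consistently coded score = 0.3 × (L7 + L8 + L9 + L10).

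**Same level on all four items.**

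| Level | Printed codes (Q7, Q8, Q9, Q10) | Printed score | Consistent score |
|---|---|---|---|
| 1 (worst) | 5, 1, 5, 1 | 12 × 0.3 = 3.6 | 4 × 0.3 = 1.2 |
| 2 | 4, 2, 4, 2 | 12 × 0.3 = 3.6 | 8 × 0.3 = 2.4 |
| 3 | 3, 3, 3, 3 | 12 × 0.3 = 3.6 | 12 × 0.3 = 3.6 |
| 4 | 2, 4, 2, 4 | 12 × 0.3 = 3.6 | 16 × 0.3 = 4.8 |
| 5 (best) | 1, 5, 1, 5 | 12 × 0.3 = 3.6 | 20 × 0.3 = 6.0 |

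A change from worst to best is 3.6 − 3.6 = 0.0 under the printed rule and 6.0 − 1.2 = +4.8 under consistent coding.

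**One-level improvements from mid-scale (all items at 3, score 3.6).**

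| Items that improve | Printed score | Consistent score |
|---|---|---|
| Q7 and Q9 only | 3.0 | 4.2 |
| Q8 and Q10 only | 4.2 | 4.2 |
| All four | 3.6 | 4.8 |

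An improvement confined to the frequency items lowers the printed score.

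**Answers that are not perfectly uniform.** There are 5 + 4 × (2⁴ − 2) = 61 patterns in which the four items lie within one level of each other. Across them the bracketed gap is at most 2 in either direction, so the printed score stays within 3.6 ± 0.6, that is 3.0 to 4.2, while the consistent score runs from 1.2 to 6.0. Over all 5⁴ = 625 patterns, equally weighted, the two scores have zero correlation.

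**Which pair is inverted.** The SAP's own items point to Q7 and Q9.

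- The PROMIS item SFLUB001, worded like Q7, is coded "5=Almost always or always 4=Most of the time (more than half the time". SFLUB004, worded like Q10, has 5 for not difficult. In the PROMIS conversion table the T-score rises with SFLUB001 at every fixed SFLUB004, from 27.6 at (1, 1) to 58.4 at (5, 5).
- All three FSFI pain items have 5 as the favourable end. Their rule, "Pain Score = (FSFIQ17+ FSFIQ18+ FSFIQ19)*0.4", gives 0.4 × 3 × 1 = 1.2 to 0.4 × 3 × 5 = 6.0, the range that lubrication has under consistent coding.
- Q17 asks "how often did you experience pain during vaginal penetration" and Q18 asks the same about pain afterwards. Both use the same five frequency labels as Q7 and Q9. For pain, 1 for almost always is rightly the bad end. This fits a list copied from the pain items but does not prove it.

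**If the data already hold 5 = almost always for Q7 and Q9.** The unreversed sum is 0.3 × 4L = 1.2 to 6.0 and is correct. Adding a reversal would then create the fault: 0.3 × [(6 − L) + L + (6 − L) + L] = 3.6 at every level. Labels taken from the printed list would be wrong for 4 of the 5 non-zero codes, because only code 3 keeps its meaning.

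**Code 0.** With all four items 0, reversing without restriction gives 0.3 × (6 + 0 + 6 + 0) = 3.6 for a woman with no sexual activity. Keeping 0 as 0 gives 0.

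**The case against.** The strongest reply concerns consequence. Harm needs two things that the documents do not settle: that the data were captured under the printed codes, and that the derived score is reported.

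- On the first, the evidence for a copied list fits a slip confined to the SAP text at least as well as miscoded data.
- On the second, the 8.6.3 sentence "Descriptive summary will also be provided using the derived subscale scores" stands under PROMIS. For FSFI lubrication and pain that section describes only counts, percentages and shifts in response. The table templates are in a separate document, and 8.6.3 also refers to a separate psychometric analysis plan.
- The 0.0 against +4.8 contrast is an extreme illustration, not an expected bias. The printed score does vary when the frequency and difficulty answers disagree.

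These points stand as limits on the impact, but they do not remove the error. One of the two printed elements, the formula or the code lists, must change whichever codes the data hold. Section 7.1 does define the score, and Section 10 lists a subscale table (14.2.3.5) apart from the all-questions table (14.2.3.6), as it does for PROMIS. That suggests, without proving, that the score will be tabulated. The psychometric plan is described only as covering validation analyses, so it cannot be assumed to correct the scoring.

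**Conclusion.** The concern holds. As printed, the FSFI lubrication score does not measure the level of lubrication: it is 3.6 at each of the five uniform levels, where consistent coding gives 1.2 to 6.0. This is certain for the printed text. An effect on results assumes that the data carry the printed codes and that Table 14.2.3.5 or 14.2.3.7 reports the score.

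The reach is narrow. The score is exploratory and outside the testing hierarchy in 8.6.1. The primary endpoint, the satisfaction endpoints based on FSFI Q16 and the PROMIS lubrication score are unaffected. The item-level Table 14.2.3.6 is also unaffected, provided its labels match the codes in the data. The point should be fixed because a stated scoring rule is wrong and the correction is cheap; it does not threaten the trial's main conclusions.

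**What to change.** Check the code list under which the FSFI was captured, then take one of two routes.

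- **Data hold 1 = almost always for Q7 and Q9:** score these two items as 6 − item for codes 1 to 5 only, and keep 0 as 0.
- **Data hold 5 = almost always:** correct the printed code lists for Q7 and Q9 and any output labels taken from them, and apply no reversal.

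In either case, state in 7.1 that among sexually active women a higher score means better lubrication and that 0 means no sexual activity. It would also help if 8.6.3 said whether Tables 14.2.3.5 and 14.2.3.7 use the derived score or the item responses.

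The cost is one code-list check and a correction of either one formula or two code lists with their labels, plus the short clarifying statements. No new data are needed.
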